Effects of Pregnenolone on Perceived Social Isolation IRB16-0834 Protocol Version July 26, 2019 NCT02826577

Effects of Pregnenolone on Perceived Social Isolation

PROJECT ABSTRACT

Perceived social isolation (PSI), also known as loneliness, has been shown to increase depression in humans and animal models and to increase the risk of early mortality by 26%. Despite the well-known effects of pregnenolone (PREG) in alleviating depressive behavioral effects of social isolation in mice and post-traumatic disorders and depressive symptomatology in humans, no studies to date have examined the effects of PREG on humans with PSI as well on a specific mechanism of action underlying PSI, such as increased hypervigilance to social threat- a vital first step in the novel use of PREG as an adjunctive therapy for attentional bias to social threats in individuals with PSI. We therefore propose a randomized, double-blind, between-subjects design, where three validated behavioral paradigms on social threats will be combined with highdensity electrical neuroimaging to probe the neuro-circuitry of social threat processing in male adults (aged 21-80) high in PSI.

1. BACKGROUND AND SIGNIFICANCE

A growing body of research suggests that the perception of social isolation (PSI, or what has been termed loneliness; Cacioppo and Patrick, 2008) has detectable effects on attention, including increased vigilance for negative social stimuli, such as social threats (Cacioppo & Hawkley, 2009; Cacioppo, Balogh, Cacioppo, 2015, Cacioppo, Bangee, et al., 2015). This focus on self-preservation may promote short-term survival but has been shown to have long-term costs for health and well-being (Cacioppo & Hawkley, 2009). For instance, using a modified emotional Stroop task, we found that lonely subjects, relative to nonlonely subjects, show greater Stroop interference specifically for negative social relative to negative non-social words (Egidi, Shintel, Nusbaum, & Cacioppo, 2008). Stroop interference has been used to gauge the implicit processing of stimuli, so these results suggest that PSI is associated with a heightened accessibility of negative social information. Similarly, in an investigation of the effects of subliminal priming on the detection of painful facial expressions, Yamada and Decety (2009) found that PSI is associated with greater sensitivity to the presence of pain in dislikable faces, as gauged by the sensitivity index, d', from signal detection theory. In an eye tracking study, lonely and nonlonely young adults viewed various positive and negative social scenes and exhibited different fixation patterns. Individuals high in PSI (or loneliness) are more likely to first fixate on and to spend a greater proportion of their initial viewing time looking at socially threatening stimuli in a social scene, whereas individuals low in PSI are more likely to first fixate on and spend a greater proportion of their initial view time looking at positive stimuli in a social scene (Bangee, Harris, Bridges, Rotenberg, & Qualter, 2014). Combining high-density electrical neuroimaging with a behavioral task including social and non-social threat (and neutral) IAPS pictures known to probe preattentional mechanism for social threats (the pre-attentional social threat task, PAST, Cacioppo, Bangee, et al., 2015), we showed that individuals *high* in PSI (N = 10) differentiate social threat images from non-social threat stimuli more quickly (~116 ms after stimulus onset) than individuals low in PSI (N = 9; \sim 252 ms after stimulus onset) brains. That speed of threat processing in lonely individuals is in accord with the evolutionary model of loneliness that indicates feeling socially isolated (or on the social perimeter) leads to increased attention and surveillance of the social world and an unwitting focus on self-preservation. Brain source estimates expanded these results by suggesting that *lonely* (but not *nonlonely*) individuals showed early recruitment of brain areas involved in visual attention and self-representation (Cacioppo, Bangee et al., 2015). The next step is to investigate how and when this early hyper-attention for social threats in individuals high in PSI may be reduced.

For the past decade, preclinical and clinical data suggest that pregnenolone may be a promising therapeutic in reducing a wide range of emotional responses from anxiety- and depressive-like behaviors. Pregnenolone is neuroprotective, reduces anxiety, and enhances learning, memory, and myelination. Treatment with pregnenolone elevates allopregnanolone (ALLO, a neurosteroid that enhances GABA_A receptor responses) and pregnenolone sulfate (a positive NMDA receptor modulator). In turn, exogenous administration of the neurosteroid allopregnanolone (ALLO) has also been shown to hold significant promises for reducing a wide range of emotional responses in humans with anxiety, depressive-like, and aggressive behaviors and inducing changes in responses to contextual fear conditioning in rodent models of emotional dysfunction in social isolation, and ALLO blockade impairs social and affective functioning. Although studies in humans are less abundant, they are broadly consistent with animal findings. For instance, cerebrospinal fluid levels of ALLO are reduced in women with major depressive disorder (MDD) and post-traumatic stress disorders (PTSD), and increase with successful

pharmacological treatment (Amin et al., 2006; van Broekhoven et al., 2003; Uzunova et al., 1998; Rasmusson et al., 2006; Strohle et al., 1999). Interestingly, various antidepressant agents (including fluoxetine, norfluoxetine, fluvoxamine and paroxetine) elevate ALLO brain levels (e.g., Uzunova et al., 1998; Romeo et al., 1998; Marx et al., 2006), leading to the suggestion that ALLO induction might be an important mechanism for the antidepressant effects of SSRIs (e.g., Pinna et al., 2006, 2009). Based on these observations, it has been suggested that ALLO dysregulation may contribute to the development of neuropsychiatric disorders, and that restoration of ALLO regulation may be a potential pathway for symptomatic improvement (Pinna & Rasmusson, 2011). Because a reduction in the synthesis of ALLO has been observed during social threat processing, potentially by reducing brain-derived neurotrophic factor (BDNF) regulation and increasing hypothalamic–pituitary–adrenal (HPA) activity through the hippocampus, amygdala, and bed nucleus of the stria terminalis (BNST (Cacioppo et al., 2015), Cacioppo & Cacioppo, 2015), we hypothesize that exogenous administration of ALLO precursor, pregnenolone, may help reduce hyperattention to social threats in PSI. Little is known, however, on the effects of oral administration of pregnenolone on hyperattention to social threat.

Historically, treatment with PREG has been found to alleviate the depressive behavioral effects of social isolation in mice and depressive symptomatology in humans by elevating ALLO. Therefore, PREG directed at up-regulating ALLO (neurosteroid deficit target) in individuals high in PSI could reduce PSI and improve its behavioral effects. The doses we propose in the current project have been shown to up-regulate ALLO: A single oral dose of 175 mg PREG approximately doubles ALLO serum levels over the course of 4–8 h, while a single oral dose of 400mg of PREG triples ALLO serum levels over the course of two hours in healthy non-psychiatric subjects with normal neuro-active steroid levels at baseline. One potential mechanism for PREG's ability to directly impact emotion neuro-circuitry is the up-regulation of ALLO in the central nervous system. Sripada and colleagues (2013), for instance, demonstrated that a single oral administration of PREG (400mg) reduces activation of brain areas involved in negative emotions, increases activity in the dorsal medial prefrontal cortex (dMPFC), and enhances connectivity between the amygdala and dMPFC, an effect that was associated with reduced self-reported anxiety. However, the effect of PREG on other negative emotional mechanisms, such as attentional bias to social threats and depressive symptomatology remains unknown. Our proposed novel use of the currently available dietary supplement, PREG, on PSI is based on formative animal work on social isolation by our colleague, [name]. In a rodent model, [name] demonstrated that: i) the exaggerated contextual fear responses expressed by socially-isolated mice can be normalized by increasing ALLO levels; ii) HPA dysfunction and impairment of hippocampal neurogenesis respectively can be normalized or prevented with the administration of exogenous ALLO either during or following a period of chronic stress (and iii) the establishment of depressive/anxiety-like behaviors in rodents can be precluded also with administration of exogenous ALLO-targeted treatment.

2. Purpose

The goal of the proposed research, which is based on prior human and animal work, is to test a proof-ofconcept that acute oral administration of PREG reduces PSI in male adults (aged 21-80) high in PSI. Validated self-report measures (e.g., depression, anxiety, objective social isolation, life satisfaction) will also be used to examine changes in symptom severity and subjective feelings. The long-term objective of this project is to advance the use of PREG at remediating the protracted reduction in the neurosteroid, ALLO in individuals high in PSI and thereby reduce PSI and improve social withdrawal. The proposed project will employ a randomized between-subjects

design, where a validated behavioral paradigm on social threat attention, intention understanding, and perception of others will be combined with validated measures of depressive symptomatology in male adults (aged 21-80) high in PSI.

Reducing PSI, attentional biases, and depressive symptomatology through the use of a pharmacological treatment may, therefore, have potential benefits for health and well-being. Until now, a main challenge for physicians and mental health clinicians has been to become sufficiently informed about the scientific definition of PSI (or loneliness) so that other mental disorders were not mistakenly diagnosed and treated when PSI was either the primary presenting problem or the cause of the depression for which treatment was sought⁴⁴. For decades, many clinicians believed that PSI was simply an aspect of depression with no conceptual distinctions worthy of study¹. There is now considerable evidence showing that PSI and depression (as well as other factors such as introversion, neuroticism, objective social isolation, & social support) are separable and that PSI increases the risk for (or leads to) depression. For instance, even after controlling for objective social isolation and other potential confounding factors, PSI contributes to a constellation of physical and psychiatric dysfunctions⁴⁴⁻⁴⁸. PSI is also a risk factor for alcoholism, suicidal thoughts, aggressive behaviors, social anxiety, and impulsivity. In addition, PSI is a risk factor for cognitive decline and the progression of Alzheimer's Disease, recurrent stroke, obesity, increased vascular resistance and elevated blood pressure, increased hypothalamic pituitary adrenocortical (HPA) activity, diminished immunity, an under-expression of genes bearing anti-inflammatory glucocorticoid response elements and an upregulation of proinflammatory gene transcripts, and premature mortality. Moreover, meta-analyses indicate that cognitive/behavioral interventions have proven to be largely ineffective. Thus, a pharmacological treatment for PSI is timely needed. Despite its public health importance, there is no pharmacological treatment for PSI. In addition, a key neurobehavioral characteristic of individuals high in PSI is an increased implicit attentional bias for social threats, which has been linked to an early evoked neurophysiological response and underlie unsuccessful social connections and social withdrawal. This focus on self-preservation reinforces Cacioppo and colleagues' seminal evolutionary model of PSI⁸ that emphasizes the role of hyper-vigilance to social threats as a mechanism promoting short-term survival but also as having long-term costs for health and wellbeing.

3. Innovation

In the present project, 224 PSI subjects will be randomized to a single oral dose of PREG 400mg (n=112), or placebo (PBO, n=112), while behavioral responses and neuro-active steroid levels will be measured *before and after* study drug/placebo administration. This project is innovative is several ways. First, it is the first study of its kind to test the effect of PREG in individuals high in PSI. Second, it strategically combines multiple lines of investigation – behavioral, psychopharmacology, neuroimaging, and advanced statistical techniques (e.g. brain microstate identification via root mean square error modeling; bootstrapping) --- often carried out separately. More precisely, the proposed study aims to test a proof-of-concept that acute oral administration of PREG reduces PSI and its depressive symptomatology and improves attentional bias for social threats in a double-blind randomized research study combining a validated behavioral paradigm on social threat attention, intention understanding, and perception of others in male adults (aged 21-80) high in PSI. Validated self-report measures (e.g., depression, anxiety, objective social

isolation, life satisfaction) will also be used to examine change in symptom severity and subjective feelings. Third, it tests multiple layers of 'target engagement' including ALLO levels (determined by the state-of-the-art gas chromatography-mass spectrometry (GC-MS) quantification technology) in serum and saliva, and behaviors, and proximal and distal clinical outcomes. Importantly, the proposed study is the first to use PREG to engage the target ALLO to improve PSI. Such research has the potential to yield important insights into the neurobehavioral mechanisms of PREG on PSI and its underlying behavioral effects--- a first key step toward the development of adjunctive PREG therapy in individuals with PSI. Moreover, the proposed project is novel as it will attempt to establish PREG, a dietary supplement, as an agent intended to remediate the protracted reduction in the neurosteroid, ALLO, as a treatment for PSI in humans. The overarching objective is to use an acute, daily oral dose of PREG as an "ALLO normalizer" for six weeks to increase the likelihood patients with PSI will benefit from PREG. If successful, the novel use of PREG has the potential to reduce PSI and provide PSI patients with relief from PSI-related symptoms and disorders.

4. Rationale for using pregnenolone (PREG), as opposed to ALLO: The rationale for a PREG approach is that PREG is an ALLO precursor that is lipophilic and readily crosses the blood brain barrier—a characteristic that makes it the first line of pharmacological treatment for PSI. PREG deficiency leads to depression and even suicide and there are also studies showing impairment of cognition and memory and replacement therapy reverses these effects. PREG is the precursor of neurosteroids and also TSPO agonists that increase levels of PREG and downstream steroids, including ALLO have been suggested for anxiety/depression treatment and tested in clinical trials and these molecules show advantages for the treatment of several neuropathologies^{63,64}. It is important to emphasize that in this study the dose-response design followed by determining the levels of neurosteroids (e.g., ALLO) aims at a normalization of the PSI-induced downregulation of the serum neuro-active steroid levels rather than increasing them to supraphysiologic levels. Therefore, measuring neuro-active steroids immediately after completion of treatment will guide eventual adjustment of doses and therefore a better utilization of resources during the Present project. The novel application of PREG in the present study is also reinforced by the compelling findings by Sripada and colleagues, who showed an acute, oral dose (400mg) of PREG up-regulate ALLO in young adults (age between 18-32) and reduce activation of brain areas underlying negative emotions processing. An alternative means of increasing ALLO would be to administer it directly. However, such approach would increase the risk of undesirable side effects (e.g., sedation) as it would globally impact ALLO levels even in brain regions where levels are physiologically low. Also, while synthetic neurosteroids (e.g., Ganaxolone) offer another potential approach, they are currently under development or require further testing for potential medical use in humans. Because SSRI, such as fluoxetine (FLX), are also known to elevate ALLO levels, a FLX approach could have been also considered. However, FLX has a low response rate, which varies from 30-50%, and a constellation of undesirable side effects. Thus, pre-clinical work signifying PREG, a generally well-tolerated dietary supplement, up-regulates ALLO suggests it is a viable approach to engage ALLO inhumans. Clinical trials that have used a PREG approach on negative emotion processing, schizophrenia, or on inflammatory diseases, consistently show that PREG 25-500 mg/day has minimal side effects, and does not affect weight, heart rate, blood pressure (even in patients with hypertension), menstrual cycle, or glucose levels (either in diabetics or non-diabetics.

Rationale for selected dose range in the present project: Here, 224 subjects high in PSI will be randomized to a single oral dose of PREG 400mg (n=112), or placebo (PBO, n=112) to ascertain dose of administration. The rationale for the selected dose range is the following: First, clinical trials showed that PREG 25–500 mg/day is safe and well tolerated in humans. Second, Sripada and colleagues made the compelling basic science discovery that a single dose (400mg) of PREG up-regulates ALLO in young adults (See Fig. 1) and reduces activation of brain areas underlying negative emotions processing.

Steroid (pg/ml)	Placebo (n=15)		Pregnenolone Group (n=16)			
	Baseline (Mean ± SD)	Endpoint (Mean ± SD)	Baseline (Mean ± SD)	Endpoint (Mean ± SD)	ï	р
Pregnenolone	1378.8 ± 579.1	1190.8 ± 468.5	1238.0 ± 378.7	3943.6 ± 696.3	12.3	<.001
Allopregnanolone	114.3 ± 49.6	118.1 ± 76.5	112.3 ± 40.9	802.2 ± 280.7	10.2	<.001
Pregnanolone	470.6 ± 200.8	490.5 ± 135.6	352.0 ± 106.6	517.4 ± 96.2	3.2	.004

Fig. 1. Steroid and metabolite levels in Sripada et al.'s 2013. *T-tests were conducted on change scores (steroid levels at endpoint minus steroid levels at baseline). Pregnenolone group received an acute, oral dose of PREG 400mg.

Based on pharmacokinetic data in humans, we expect the peak serum concentration of ALLO to occur approximately 2 hours after acute, oral administration of PREG 400mg. Saliva levels will be measured at the following 3 time points: -0.5, 2.0, 3.0 to provide various measures and correlations with behavioral tasks and correlations with serum levels.

4. Aims & Hypotheses:

Specific Aim 1: Assess PREG on levels of ALLO in a dose-finding design. Relative to PBO, PREG will dose-dependently increase and normalize ALLO levels in individuals high in PSI such that it will be comparable to Matched Healthy Controls (MHC) (Hypothesis 1A).

Specific Aim 2: Examine PREG on attentional bias to social threats and depressive symptomatology in individuals who are high in PSI. Relative to PBO, PREG will reduce depressive symptomatology and attentional bias to social threats and improve intention understanding and perception of others in individuals high in PSI (Hypothesis 2A). Hypothesis 2B: In PSI and MHC, depressive symptomatology and attention to social threats will correlate negatively with ALLO levels.

5. Duration of the study: The total duration of the entire study on campus is between 4 and 4 $\frac{1}{2}$ hours maximum.

6. Location of the study:

The entire study will be performed at the University of Chicago Department of Psychiatry and the University of Chicago Center for Cognitive and Social Neuroscience Center's High-Performance Electrical Neuroimaging (HPEN) Laboratory ([name]) on a 128-channel EGI system with 1000 HZ sampling rate.

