7. RESEARCH METHODS

The Approach

This project will comprise a randomized, placebo- controlled, between-subjects design, where we will couple a validated behavioral paradigm on attention to social threats with an acute pharmacological challenge with oral pregnenolone (PREG) or placebo (PBO) in subjects high in PSI and test behavioral responses and neuro-active steroid levels *prior and after study oral drug administration*. In the present project, 224 PSI subjects will be randomized to a single oral dose of PREG 400mg (n=112), or placebo (PBO, n=112) to ascertain dose of administration. In this project, participants will attend a single laboratory visit. During this single session, behavioral responses and subjective feelings will be tested at two time points (once before and once after). Neuro-active steroids will be measured from blood and saliva at several points to ascertain they correlate. A group of Matched Healthy Controls (MHC) who are low in PSI (n=12) and will not receive PREG but will otherwise complete all questionnaires of the study. Participants will be recruited from the University of Chicago and in the community.

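### Aim 1 claims dose-finding and normalisation of ALLO to control level, but the trial has one active dose, no definition of comparable, and no planned ALLO comparison

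*Combined protocol and SAP*

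**What the plan says.** Specific Aim 1 (section 4, Aims & Hypotheses) reads "Assess PREG on levels of ALLO in a dose-finding design". Hypothesis 1A, under it, is a prediction relative to placebo: "PREG will dose-dependently increase and normalize ALLO levels in individuals high in PSI such that it will be comparable to Matched Healthy Controls".

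The same idea appears elsewhere. The rationale for using pregnenolone rather than ALLO says "in this study the dose-response design followed by determining the levels of neurosteroids", and states that the aim is to normalise levels "rather than increasing them to supraphysiologic levels". It adds that "measuring neuro-active steroids immediately after completion of treatment will guide eventual adjustment of doses". The dose paragraph opens with "The rationale for the selected dose range is the following".

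The design itself is stated in section 7, The Approach: "224 PSI subjects will be randomized to a single oral dose of PREG 400mg (n=112), or placebo (PBO, n=112) to ascertain dose of administration". Section 3, the dose paragraph and C.2.5 give the same two arms, and the drug factor in the C.2.7 analyses has the same two levels. The 12 matched healthy controls (MHC) receive no drug.

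On ALLO, the first of the two sections numbered C.2.6 (Neurosteroid Analyses) describes serum before dosing and two hours after, with the assay. The dose paragraph expects the serum ALLO peak at about 2 hours.

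**The concern.** Aim 1 is the target-engagement aim: it asks whether the drug moves the steroid through which it is supposed to act. It makes three claims, and each has a gap.

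- **Dose-dependence.** This needs at least two active doses, and there is one.
- **Comparability to MHC.** Without a margin or a time point, this can be neither met nor missed. A non-significant difference against 12 controls would not establish it.
- **A rise against placebo.** The design can answer this, but C.2.7 contains no analysis of it.

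The risk is a report that claims a dose-response or a normalisation which the data could not have tested, while the one answerable comparison has no pre-stated form.

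**Working it through.** **1. Number of active doses.** Every statement of the randomisation gives PREG 400 mg or placebo, 112 each. Participants attend one visit and take one dose. The remark about later adjustment of doses supplies no second dose and no adjustment rule. So there is one active-versus-placebo contrast and no contrast between doses.

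**2. The protocol's own Fig. 1 for ALLO (pg/ml, mean ± SD).** Placebo (n=15) went from 114.3 ± 49.6 to 118.1 ± 76.5. PREG 400 mg (n=16) went from 112.3 ± 40.9 to 802.2 ± 280.7. The stated test statistic is 10.2, on change scores.

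Reproducing that statistic first:
- Difference in change = (802.2 − 112.3) − (118.1 − 114.3) = 689.9 − 3.8 = 686.1.
- SD of change in each arm = √(s₁² + s₂² − 2·r·s₁·s₂), where r, the within-person correlation, is not given. The pooled t is 8.9 at r = 0, 9.8 at r = 0.5 and 10.5 at r = 0.8. The stated 10.2 fits.

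Size of the rise:
- 802.2 / 112.3 = 7.1-fold over baseline.
- 802.2 / 114.3 = 7.0 times the placebo group's baseline, and 802.2 / 118.1 = 6.8 times its endpoint.

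**3. Fig. 1 against the hypothesis.** Serum in this trial is drawn at the expected peak after the same dose. A level about seven times untreated is hard to square with being comparable to untreated controls, or with avoiding supraphysiologic levels. Section 1 gives a smaller figure, a threefold rise after 400 mg, in healthy subjects with normal baseline levels. In such people that would still end at about three times normal. Whether high-PSI men would end near control level depends on how low they start, and the documents give no ALLO value for them.

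**4. What C.2.7 analyses.** The MANOVA covers demographic and behavioural measures. The 2 × 2 ANOVA covers questionnaire scores. The 2 × 2 × 2 ANOVA covers reaction times and valence ratings. The ALLO analyses mentioned anywhere are correlations: blood with saliva, saliva with behavioural tasks, and ALLO with symptoms and attention (Hypothesis 2B). None compares ALLO between PREG and placebo, or with MHC.

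**5. Would the PREG-versus-placebo answer be at risk?**
- At the Fig. 1 effect: SE = 686.1 / 10.2 = 67.3; SD of change = 67.3 / √(1/15 + 1/16) = 187; d = 686.1 / 187 = 3.7. Power is over 99% with 112 or with 12 per arm. (12 per arm is an assumption: the power paragraph's total of 36, divided by three groups.)
- At a threefold rise, keeping the Fig. 1 coefficients of variation: log SD = √ln(1 + CV²), which at endpoint is 0.34 for PREG (CV 280.7/802.2 = 0.35) and 0.59 for placebo (CV 76.5/118.1 = 0.65). The pooled value is √((0.34² + 0.59²)/2) = 0.48, and d = ln 3 / 0.48 = 2.3. Power at 12 per arm is over 99.9%.
- With log change scores and zero within-person correlation, the baseline log SDs of 0.35 and 0.42 are added in. The pooled SD is 0.62, d = 1.8, and power at 12 per arm is 98.6%.

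**The case against.** The best defence is that the ALLO comparison is under-specified rather than absent. Hypothesis 1A names placebo as the comparator. Section 7 says steroid levels are tested before and after dosing. C.2.6 fixes serum at pre-dose and 2 hours so that results can be set beside the Fig. 1 study, which used t-tests on change scores. This largely stands: the contrast and the time are recoverable, and only the scale and the baseline adjustment are open. A reader might infer that the time point would be picked after the data are seen; the text on the 2-hour peak and the 2-hour serum sample does not support that.

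A reader might also infer that normalisation at 400 mg must fail. The documents do not support that either. Fig. 1 comes from another study, in adults aged 18-32; no high-PSI baseline is given; and the threefold figure points to a smaller rise. Tension is the most that can be said.

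A third tempting inference is that 36 subjects would be too few for PREG versus placebo if the rise were only threefold. That requires carrying the change SD of 187, which comes mainly from an arm with mean 802, over to a mean less than half as large. With the coefficient of variation kept, power stays above 98%.

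None of this rescues the dose-response wording or supplies a margin.

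**Conclusion.** The point holds and should be fixed. With one active dose, the dose-finding aim and the dose-dependent part of Hypothesis 1A cannot be tested; this is certain from the text. It is equally certain that comparability to MHC has no margin and that C.2.7 contains no ALLO comparison by treatment or against MHC. The doubt about normalisation is a matter of degree: a 7.1-fold rise in Fig. 1 against an unstated high-PSI baseline. It assumes that the Fig. 1 response carries over to men aged 21-80 high in PSI.

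The consequence is limited. The PREG-versus-placebo conclusion is unlikely to change, given d of about 3.7 at the Fig. 1 effect and about 1.8 to 2.3 on the log scale at a threefold rise. What is at stake is which claims the report may make.

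**What to change.** 1. Delete the dose-finding, dose-dependent and dose-response wording, and the phrase about ascertaining the dose, wherever they occur. Change dose range to dose. Restate Hypothesis 1A as PREG 400 mg versus placebo.
2. Add one primary ALLO analysis to C.2.7: log serum ALLO at 2 hours, PREG versus placebo, adjusted for pre-dose log ALLO, with a 95% CI.
3. Drop the claim of normalisation to MHC level. Report ALLO in PSI subjects against MHC, pre-dose and at 2 hours, descriptively with CIs. Reword the sentence on supraphysiologic levels to match.

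Two minor alignment notes: section 7 lists three blood draws where C.2.6 lists two serum samples, and the threefold rise in section 1 should be reconciled with Fig. 1. The blood-saliva correlation and Hypothesis 2B need no change.

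The cost is protocol wording and one analysis line, with no change to randomisation, sampling or data. The sponsor gives up the dose-response and normalisation claims, which this design cannot support.
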